University of Chicago Medical Center Research Protocol

Principal Investigator: [name] – Pediatrics/Neonatology &
Medicine/Gastroenterology

Other Investigators: [name], MD – Pediatrics/Neonatology
[name] – Pediatrics/Infections Diseases

Study Title: Antibiotic stewardship and protection of the developing preterm infant microbiome

ABSTRACT:

Fear of early-onset sepsis (EOS) has led to nearly universal initiation of empiric antibiotics at birth in preterm infants. While the risk of morbidity and mortality from EOS is high, the frequency is low at 0.98 per 1000 live births (Stoll et al 2011). Evidence shows that there are significant risks involved with prolonged antibiotic therapy, including necrotizing enterocolitis, invasive fungal infection, and even death. Furthermore, antibiotics alter the microbiome, which is increasingly being recognized as a key determinant of health and disease. The development of the microbiome begins at birth; the very time empiric antibiotics are begun in the majority of preterm infants. We hypothesize that antibiotic stewardship principles can be used to limit empiric antibiotic use at birth in preterm infants, thus leading to protection of the developing microbiome and improved clinical outcomes.

I. Aim and Hypotheses

Preterm infants are frequently started on empiric antibiotics at birth due to the risk of early onset sepsis (EOS). While the risk of morbidity and mortality from EOS is high, the frequency is low at 0.98 per 1000 live births (Stoll et al 2011). There are risks involved with antibiotic therapy including disseminated fungal infection, neonatal necrotizing enterocolitis, and alteration of the gastrointestinal microbiome (Nash et al 2009). We hypothesize that antibiotic stewardship principles can be used to limit empiric antibiotic use at birth in preterm infants, thus leading to protection of the developing microbiome and improved clinical outcomes.

Aim 1: Implement an antibiotic stewardship program to limit initial empiric antibiotic administration in a pilot study group of 30 preterm patients, 28-34 weeks gestation.

Aim 2: Evaluate outcomes in infants who do, or do not, receive empiric antibiotics at birth. Blood culture results, clinical outcomes, length of stay, total days of antibiotics received during NICU admission, and microbiome development from birth until hospital discharge will be examined.

II. Background and Rationale

A. Background:

Greater than 12% of infants in the United States are born premature and may begin their lives within the neonatal intensive care unit (Matthews et al). Within this population, the evaluation and treatment for early-onset sepsis (EOS) is an ongoing controversy. EOS remains the leading cause of morbidity and mortality in neonates with a rate of 0.98 per 1000 live births (Stoll et al). Infants admitted to NICUs are frequently started on empiric antibiotics due to the risk of EOS. Although the CDC has released algorithms for the evaluation of EOS for all newborns, without a lower gestational age limit indicated to which they apply, clinical experience has shown that nearly all premature infants receive empiric antibiotics (Verani et al 2010). Recent algorithms by the AAPs Committee on the Fetus & Newborn recommend discontinuing empiric therapy at 48 hours with negative cultures in preterm infants (Polin et al 2012). However, although it has been shown that discontinuing antibiotics when cultures are negative in asymptomatic ELBW infants does not compromise clinical outcomes, they often receive prolonged antibiotic treatment courses (Cordero & Ayers 2003). Furthermore, Kuppala et al (2011), studied very low birth weight (VLBW) infants, and found that within their population, 16% did not receive empiric antibiotics. For those who were treated, each day of initial empiric antibiotic therapy significantly increased the odds of developing late-onset sepsis (LOS), NEC or death, and for infants who had received any initial empiric antibiotic exposure, the number needed to harm was 3.

Within our unit, there were 794 admissions in 2014. Of these, 196 were within our study's target age range of 28-34 6/7 weeks of gestation at birth. While there were no positive blood cultures at birth within this gestational age range, only 6 of these 196 patients did not receive empiric antibiotics at birth. Additionally, of the 190 that were treated, 43 were treated beyond the standard 48-hour rule-out-sepsis recommendations.

Recently, there has been a growing body literature describing the effects of antibiotics on the gastrointestinal microbiome. In a study of 26 patients in 2009, Tanaka et al. found that the neonates that has received either oral or intravenous antibiotics during the first 4 days of life had less gut microbial diversity, as well as an attenuation in colonization with *Bifidobacterium* and an increase in colonization with *Enterococcus*. Additionally, a study by Fouhy et al showed that infants exposed to the empiric antibiotics ampicillin and gentamicin shortly after birth tend to develop microbiomes with higher proportions of *Proteobacteria*, *Actinobacteria*, and *Lactobacillus* than the unexposed infants for up to a month following the treatment course.

These changes within the microbiome may be especially important within the premature population, where Wang et al (2009) found that infants who developed necrotizing enterocolitis (NEC) had significantly more days of antibiotics prior to disease onset, as well

as differences in their gastrointestinal microbiome, having less microbial diversity and an increased abundance of *Gammaproteobacter*. Similarly, Cotton et al (2009) has also shown that prolonged antibiotic therapy (>5 days) was associated with increased odds of NEC or death. In earlier studies, Cotton et al (2006) linked prolonged broad spectrum antibiotic therapy with increased risk for invasive fungal infections. Beyond the immediate neonatal timeframe, gastrointestinal microbial dysbiosis has also been linked to multiple diseases affecting long term health, including inflammatory bowel disease (IBD), obesity, asthma and atopy (Arietta et al 2014).

Due to the effects of the microbiome health and disease, as well as growing concerns for antibiotic resistance, there has been a growing recognition for the need for antimicrobial stewardship. According to the Infections Diseases Society of America (IDSA), antimicrobial stewardship includes interventions targeted toward the improvement and monitoring of appropriate antimicrobial use by selecting the most optimal drug regimen, including the type of drug used, the dose, the duration of therapy and the route of administration. While studies have found that, in general, antibiotic stewardship is not commonly used within pediatric hospitals (Hersh et al 2009), Comer Children's Hospital has a strong, multidisciplinary antimicrobial stewardship team with an active presence within the NICU. These collaborations are necessary to promote proper and safe use of antibiotics, as Grohskoph et al (2005) found that as many as 47% of infants within NICUs were on at least one antibiotic, and Clark et al (2006) found that antibiotics are the most prescribed medications within NICUs. Within our NICU at Comer, 30-40% of patients are on at least one antibiotic on a given day (Nash et al 2014). While there is less published literature on the presence of antibiotic resistant organisms (AROs) within NICUs, de Man et al (2000) found that infants treated with cefotaxime as initial empiric therapy were 18 times as likely to grow resistant organisms.

Limiting initial empiric antibiotic therapy is one way to promote healthy gastrointestinal microbiome development, as well as limit the presence of AROs. While there is little data supporting the withholding of initial antibiotics in neonates, the administration of empiric antibiotics has been questioned for decades. In 1961, William Blanc questioned the safety of empiric antibiotics, stating "The diagnosis of congenital and early neonatal infections is difficult, and the systemic prophylactic administration of antibiotics is potentially harmful. Its dangers have to be weighed against the risk of infection." More recently, Tagare et al (2010) found that in low risk preterm neonates there was no evidence that routine empiric antibiotic use had a protective effect in clinical sepsis, further questioning the immediate use of antibiotics at birth.

B. Rationale:

Evaluation and treatment for EOS is an ongoing controversy in neonatology. While the risk of morbidity and mortality from EOS is high, the frequency is low at 0.98 per 1000 live births (Stoll et al 2011). Although the CDC has released algorithms for the evaluation of EOS for all newborns, there are no specific algorithms for preterm infants, and clinical

experience has shown that nearly all premature infants receive empiric antibiotics (Verani et al 2010). Recently, there has been growing literature on the detrimental effects of antibiotics on the development of the gastrointestinal microbiome. Important in the premature population, Wang et al (2009) found that infants who developed NEC had significantly more days of antibiotics prior to disease onset, as well as differences in their microbiome. Cotton et al (2009) has also shown that prolonged antibiotic therapy (>5 days) was associated with increased odds of NEC or death. Additionally, the microbiome has been linked with long-term health outcomes, such as asthma, obesity and IBD. With this growing body of evidence suggesting potential harm associated with empiric antibiotic exposure by preventing healthy microbialization, and the growing numbers of infections with antibiotic resistant organisms (Bizzarro & Gallagher 2007), it is critical to develop guidelines to limit antibiotic use in premature infants, and study the effect on clinical outcomes and the microbiome development.

III. Research Plan

Methods:

Through literature review and expert input, inclusion and exclusion criteria for randomization have been developed and reviewed to allow preterm infants, with a low risk of infection, to be closely observed and monitored, rather than receive routine empiric antibiotics on admission to the NICU.

Inclusion Criteria for randomization:

- 1) Infant must be born between the gestational ages of 28 0/7 weeks and 34 6/7 weeks
-AND-
- 2) Infant must be considered to have a low risk of infection by one of the following criteria:
 - a. Delivered for maternal indications (Cesarean section or induction of labor for maternal health, including HELLP, pre-eclampsia, placental abruption, history of IUFD/abruption, multiple gestation requiring preterm delivery, etc)
-OR-
 - b. Delivered due to preterm labor to a mother without the diagnosis of chorioamnionitis/maternal fever or prolonged rupture of membranes >18 hours

Exclusion Criteria:

- 1) Signs of clinical illness within the first 3 hours of life (Escobar et al 2014):
 - a. 5-minute Apgar <5
 - b. Requiring vasoactive drugs
 - c. Seizures
 - d. Significant respiratory distress requiring supplemental oxygen >40%
- 2) I:T Ratio of >0.2 on initial CBC
- 3) Congenital anomalies, including renal anomalies requiring serum antibiotic level monitoring.

30 patients who meet inclusion criteria will be enrolled for randomization. Parents of infants that may be eligible will be consented prior to the birth if the infant meets the inclusion criteria at the time of birth, they will be randomized into one of the study groups. Parents who consent will be notified whether or not their child met inclusion criteria and were randomized in the study. They can choose to withdraw their child from the study at any time.

If infants are not determined to be low-risk at the time of birth, and do not meet the inclusion criteria for randomization, they will remain in the study for stool sample analysis and data collection. Their medical management will be ordered by the primary care team, including the possible administration for antibiotics at birth.

The study design will be a randomized, double-blinded study where all consented infants who meet the inclusion criteria will undergo a standard limited sepsis evaluation at birth, consisting of a blood culture and complete blood count with differential, as recommended in the CDC guidelines for prevention of GBS sepsis. Following evaluation, infants will be randomized. The control group of infants will receive current standard of care empiric antibiotic coverage with ampicillin and gentamicin. The infants in the intervention group will receive placebo at the same dosing intervals of the routine antibiotic coverage. Antibiotics, or placebo, will be discontinued after 48 hours, at which time the blood culture would be reported as negative at 48 hours, consistent with the standard of care rule out sepsis evaluation. Each treatment group, control and intervention, will have 15 study participants. We will further aim to have half in each treatment group to be under the gestational age of 32 weeks and half older than 32 weeks. Multiples will be randomized to the same treatment group. We will consent up to 80 patients in order to have 30 that will meet randomization criteria.

If at any time during the initial 48 hour trial period an infant shows clinical signs of sepsis, as defined below, or the initial blood culture becomes positive, the infant will be unblinded. Repeat evaluation will be performed, and antibiotics will either be initiated for those in the intervention group, or appropriately broadened, per the discretion of the medical team, for those already receiving antibiotics. These patients will remain in the study for intention-to-treat analysis

Signs of clinical sepsis for which to unblind infant from the study and repeat evaluation (Hofer et al 2012, Bekhof et al 2013)

- Temperature Instability (Rectal, $>38.5^{\circ}\text{C}$, $<36.0^{\circ}\text{C}$ or $>1.5^{\circ}\text{C}$ change in 3 hours)
- Increased respiratory support of more than 20% increase in oxygen
- Pale/dusky skin tones
- Prolonged capillary refill time
- Lethargy
- Development of Seizures
- Requiring vasoactive medications for cardiovascular support
- Other signs of illness per the discretion of the managing team

Throughout their entire hospitalization, all infants will receive routine neonatal care per the medical team managing the patient.

During the entire hospitalization of the patients, daily stool samples will be collected from the infant diaper as available from spontaneous defecation, for analysis of the fetal microbiota through 16S rRNA gene-based analysis, as previously described by Wang, et al (2009). Through this stool analysis, the development of the fetal microbiome from birth through discharge will be examined and compared between the infants who do, or do not, receive empiric antibiotics at birth. Some of the stool samples will also be shared with the investigators at the University of Guelph in Ontario, Canada for further analysis, including identification of certain metabolites and antibiotic levels. The samples that are sent will be deidentified. Parents may be contacted when the infants are 18 months of life to answer a short health questionnaire about hospitalizations and chronic illnesses, as well as to provide stool samples for further analysis to determine if the differences persist once they are outside of the hospital environment. All supplies for stool samples and return postage will be provided to the parents. Parents will receive a small monetary compensation (\$15 gift card) for returning the questionnaire and stool sample.

In addition to analyzing the microbiome, blood culture results, clinical outcomes (chronic lung disease, retinopathy of prematurity, intraventricular hemorrhage, death, NEC), length of stay, initiation and type of feeds, feeding tolerance and total days of antibiotic use will be examined through review of the EMR.

Monitoring:

The study team will report all events in accordance with IRB policies and procedures. Events not meeting reporting criteria will be provided at the time of continuing review.

All enrolled infants will be continuously monitored for signs of infection during the first 48 hours of life, as well as through the remainder of their hospitalization due to their admission in an ICU setting. Because of the small size of this pilot study, if there is any adverse event or safety concern, it will be immediately analyzed.

In addition, we will meet to evaluate for adverse events and safety for every 3 patients that are enrolled into the randomization portion of the study (weekly may be impractical due to the varied response in consent among our patient population - there may be many weeks without new study participants). This will result in 10 meetings throughout the course of the pilot study. We will also invite the NICU's medical director to participate in these meetings to ensure patient safety.

We will not be performing an interim efficacy analysis. This is due to the small sample size and single site design, as well as their prematurity of our study population which requires prolonged hospitalization. The study subjects will be continuously and closely monitored due to their gestational age and hospitalization within an intensive care setting. If at any time a patient becomes ill during the initial 48 hours, they will become unblinded. If it is a

repeated pattern that only those patients who are receiving placebo are becoming ill, the safety of the study will be reevaluated by the study team.

If three patients from this group develop sepsis in the first 48 hours, the trial will end.

Works Cited

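### The bar on maternal chorioamnionitis, fever and rupture of membranes beyond 18 hours applies to only one of the two low-risk entry routes

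*Protocol*

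**What the plan says.** The Methods paragraph of III. Research Plan gives the purpose of the entry criteria: "to allow preterm infants, with a low risk of infection, to be closely observed and monitored, rather than receive routine empiric antibiotics".

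Inclusion criterion 2 puts this into practice: "Infant must be considered to have a low risk of infection by one of the following criteria". Two routes follow, joined by OR:

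- **2a:** "Delivered for maternal indications (Cesarean section or induction of labor for maternal health", followed by an open-ended list of non-infectious examples that includes pre-eclampsia and multiple gestation.
- **2b:** "Delivered due to preterm labor to a mother without the diagnosis of chorioamnionitis/maternal fever or prolonged rupture of membranes >18 hours".

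There are three exclusion criteria: signs of illness in the infant in the first 3 hours (low 5-minute Apgar, vasoactive drugs, seizures, high oxygen need), "I:T Ratio of >0.2 on initial CBC", and congenital anomalies. Infants who pass are randomised to ampicillin and gentamicin or to placebo, with treatment stopped after 48 hours.

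**The concern.** The protocol treats chorioamnionitis, maternal fever and rupture beyond 18 hours as incompatible with low risk, but attaches that test to preterm labour alone. Route 2a is defined by why the mother was delivered, and its examples are non-infectious, so delivery because of infection is not the gap. The gap is the mother with a non-infectious indication who also has one of these factors. Route 2a expressly includes induction, and an indication settled before labour does not describe her state at birth.

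At stake is the entry definition on which withholding antibiotics rests. An infant who fails the protocol's own standard under one route could, under the other, receive up to 48 hours of placebo. Because the trial is double-blind, the clinical team would not know which treatment the infant was receiving unless an unblinding trigger occurred.

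**Working it through.** The plan states no figure on this point, so the check is mainly one of logic.

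**1. The rule as written.** Eligible = gestation 28 0/7 to 34 6/7 weeks AND [2a OR (preterm labour AND no chorioamnionitis/fever AND no rupture >18 h)] AND none of the three exclusions.

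**2. Truth table for a well infant in the gestational window with no exclusion.**

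| Chorioamnionitis or fever | Rupture >18 h | Eligible by 2a | Eligible by 2b |
|---|---|---|---|
| No | No | Yes | Yes |
| Yes | No | Yes | No |
| No | Yes | Yes | No |
| Yes | Yes | Yes | No |

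Route 2a admits 4 of 4 combinations; route 2b admits 1 of 4.

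**3. Does another rule close the gap?** The exclusions concern the infant's clinical signs, the infant's blood count and congenital anomalies. None refers to the mother. The protocol mentions infants not judged low risk at birth, but low risk is defined only by criterion 2, and no separate clinician veto is written.

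**4. Size.** The document gives no rate of these factors among deliveries for maternal indications, so no expected number can be calculated and none is assumed here. It does fix the following:

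- Planned allocation is 15 and 15, so an affected infant has a 15/30 = 1 in 2 chance of placebo.
- One affected infant on placebo is 1/15 = 6.7% of that arm.
- "Multiples will be randomized to the same treatment group". An affected twin pair on placebo would be 2/15 = 13.3% of the arm, counting infants.

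**5. Background risk.** II. Background reports no positive blood culture at birth among 196 infants of this gestational range in the unit in 2014. The exact one-sided 95% upper limit is 1 − 0.05^(1/196) = 0.015, or 1.5%. This assumes that all 196 were cultured, which the text does not say. The figure is not split by maternal risk factor.

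**6. The rule after correction.** If the bar covers both routes, route 2a admits 1 of 4 combinations, the same as 2b. Sample size and analysis do not change.

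**The case against.** The best defence is that the difference between the routes may be deliberate. Preterm labour can itself be a sign of infection, whereas delivery for maternal health usually is not, so a stricter test in 2b is reasonable, and the protocol says the criteria drew on literature and expert input. A clinician following the stated intent could also decline to call the infant of a febrile mother low risk. This softens the gap but does not close it. Criterion 2 makes either route sufficient, and the protocol gives no reason why these factors would matter less when delivery is for a maternal indication.

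Safeguards also exist. Before randomisation, infants with early illness or a raised I:T ratio are excluded, and a blood culture is taken. Afterwards there is intensive-care monitoring, unblinding on clinical signs, on a positive culture or at the team's discretion, a safety meeting after every three randomised infants, and a stop after three sepsis cases. These limit harm, but they respond to the infant's findings. They do not keep a well but exposed infant out of the randomised group.

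Three further points stand. The affected group is narrow and may be empty in a pilot of 30. The shares of an arm given above would be the same for any eligibility error, so they show what one case means and not how often it occurs. And since affected infants would be randomised like any others, no bias between arms follows.

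**Conclusion.** The concern holds. As written, a well infant entering by route 2a whose mother had chorioamnionitis, fever or rupture beyond 18 hours is eligible for placebo, although the protocol rejects the same infant after preterm labour. That conclusion rests on the text alone.

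The practical consequence is uncertain. The frequency is unknown and the absolute risk of early sepsis is probably low, although the unit's 0 in 196 cannot show that exposed infants share that low risk. This is a matter of eligibility and safety, not of the validity of the comparison. It should be fixed because antibiotics are being withheld from preterm infants and the correction costs little.

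**What to change.** Make the existing clause common to both routes: (2a OR 2b) AND no diagnosis of chorioamnionitis or maternal fever AND no rupture of membranes beyond 18 hours. Listing the same factors as a fourth exclusion criterion is equivalent.

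The cost is a one-line amendment and slightly slower recruitment. The plan states: "We will consent up to 80 patients in order to have 30 that will meet randomization criteria". That is a yield of 30/80 = 37.5%, so each infant moved out needs about 1/0.375 = 2.7 further consents. Because 80 is a ceiling, replacements could use up some of that margin. The infants are not lost to the study: for those not randomised, the protocol says "they will remain in the study for stool sample analysis and data collection".

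### Does the three-hour exclusion window allow infants who fall ill early to be dropped after randomisation?

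*Protocol*

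**What the plan says.** All the relevant text is in section III of the protocol.

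- **Status of the criteria.** Methods opens by saying that "inclusion and exclusion criteria for randomization have been developed and reviewed". They are rules for entry to the randomised comparison.
- **Exclusion 1.** It covers "Signs of clinical illness within the first 3 hours of life": a low 5-minute Apgar score, vasoactive drugs, seizures, or respiratory distress with supplemental oxygen above 40%. Exclusion 2 is an I:T ratio above 0.2 on the first blood count.
- **Enrolment.** Parents consent before birth, and "if the infant meets the inclusion criteria at the time of birth, they will be randomized into one of the study groups". Up to 80 are to be consented so that 30 qualify.
- **Sequence.** Infants "will undergo a standard limited sepsis evaluation at birth" (blood culture and blood count), and then "Following evaluation, infants will be randomized". No hour of life is given.
- **Illness after allocation.** The unblinding rule begins "If at any time during the initial 48 hour trial period an infant shows clinical signs of sepsis". Such infants are unblinded and re-evaluated, and they stay in the intention-to-treat analysis. The listed signs include seizures and "Requiring vasoactive medications for cardiovascular support".
- **Monitoring.** Infants are "continuously monitored for signs of infection during the first 48 hours of life". Three sepsis cases in that period, in what reads as the placebo group, end the trial.

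**The concern.** Exclusion 1 cannot be fully assessed until three hours have passed, while the enrolment sentence speaks of the time of birth and the sepsis evaluation is also done at birth. Suppose an infant is randomised at one hour and needs vasoactive drugs at two. Read literally, the exclusion covers that infant, and so does the unblind-and-retain rule. The protocol does not say which takes precedence.

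If the exclusion were applied, an infant would be removed after allocation because of an event that withholding antibiotics might influence, and possibly after the arm had been revealed. That would undermine intention-to-treat, and it could take an early deterioration out of the safety review and out of the three-case count. With 15 infants per arm, each one removed is 1/15 = 6.7% of the arm.

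**Working it through.** **Step 1: the order of events in the text.** The protocol states no figure on this point, so the main check is a reading of the sentences together.

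- The criteria are described as criteria for randomisation. A criterion for randomisation is applied before allocation and has no role after it.
- Exclusion 2 needs a blood-count result, so allocation cannot literally take place at birth. It has to wait for at least part of the screen, which agrees with "Following evaluation, infants will be randomized".
- The enrolment sentence names only the inclusion criteria. If it were a complete rule for when to randomise, infants meeting any exclusion would be randomised too, which cannot be meant. Its reference to birth fits the moment when gestational age and reason for delivery become known.
- Consenting up to 80 to obtain 30 describes screening first and randomising second.
- No sentence removes an infant after allocation. The non-randomised group kept for stool samples and data is defined as infants not found to be low-risk at birth. It is not described as a destination for infants already allocated.
- Seizures and vasoactive drugs can properly bar entry before allocation and trigger unblinding after it. The oxygen items differ: above 40% supplemental oxygen for exclusion, an increase of more than 20% for unblinding.

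Two readings result:

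| Allocation takes place | A listed sign then appears | Rule that applies |
|---|---|---|
| After hour 3 | After allocation | Unblind and retain; exclusion window already closed |
| Before hour 3 | After allocation, before hour 3 | Unblind and retain is the only rule written for allocated infants |

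Both readings keep the infant.

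**Step 2: the effect if the text were misapplied.** Inputs:

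- n = 15 per arm and a stop at 3 cases (protocol).
- p, the sepsis risk in the placebo arm (assumed).
- f, the share of cases arising early enough to be dropped (assumed). If cases are spread evenly over 48 hours and the whole window is lost, f = 3/48 = 6.25%.

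The formula is P(stop) = P(X ≥ 3), where X is binomial with n = 15 and q = p(1 − f).

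Worked case, p = 0.20 and f = 0:

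- P(X=0) = 0.8^15 = 0.0352
- P(X=1) = 15 × 0.2 × 0.8^14 = 0.1319
- P(X=2) = 105 × 0.04 × 0.8^13 = 0.2309
- P(X ≥ 3) = 1 − 0.3980 = 0.602

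| Assumed p | f = 0 | f = 6.25% | f = 25% | f = 50% |
|---|---|---|---|---|
| 0.05 | 0.036 | 0.031 | 0.017 | 0.006 |
| 0.10 | 0.184 | 0.160 | 0.097 | 0.036 |
| 0.20 | 0.602 | 0.554 | 0.396 | 0.184 |

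The loss is small when cases are evenly spread and large only when both the risk and the early clustering are high. The protocol's own background figures point to a low risk: 0.98 early-onset sepsis cases per 1000 live births, and no positive blood cultures at birth among 196 infants of the target gestational age in the unit in 2014. At p = 0.01 the stop is almost never reached whatever is dropped (0.0004 with f = 0).

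The table also treats every dropped illness sign as a dropped sepsis case. The stopping rule counts sepsis, and a sign on the exclusion list need not be sepsis. The table therefore overstates the effect.

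**The case for a change.** The strongest case for a change is that the timing of eligibility and allocation belongs in the protocol and should not be left to an analysis plan. The enrolment wording leans towards early allocation, and nothing obliges staff to wait until hour 3. If a listed sign appears in the overlap, the infant is unblinded, so a decision to call the infant ineligible could be made with the arm known. A non-randomised group already exists into which such an infant might be reclassified. In a trial of 30, one such decision matters.

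Part of this stands. The protocol does not say whether allocation waits for the three-hour window to close, and a sentence saying so would be harmless. The rest requires someone to apply an entry criterion after entry, against the retention rule that the protocol states for exactly this situation. That would be a departure from the plan, and it could affect either arm.

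**Conclusion.** The concern does not call for a change. The hour of randomisation is unstated, but the text never directs that an allocated infant be excluded, and its one rule for illness after allocation already keeps that infant for intention-to-treat. Following the plan as written gives the result that a correction would seek, and trial staff and analysts can fill the timing gap sensibly.

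A fall in the chance of stopping from 0.602 to 0.396 is correct arithmetic, but it rests on a 20% sepsis risk and a quarter of cases arising in the first hours, neither of which comes from the protocol. Under even spread the fall is 0.602 to 0.554 at 20% and 0.036 to 0.031 at 5%, and it occurs only if the retention rule is ignored. These figures also assume that the three-case rule refers to the placebo arm and that every dropped sign is sepsis.
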